10.3.5.2. Subgroup Analyses

The following subgroups will be analyzed using the efficacy estimand to evaluate consistency of treatment effects on the primary efficacy measure if there are sufficient numbers of patients in each treatment by subgroup (for example, 10%):

- Age (<65, ≥65 years and <75, ≥75 years and <65, ≥65 to <75, ≥75 to <85, ≥85 years)
- HbA1c stratum (≤8.0%, >8.0%)
- Sex (male or female)
- BMI (<25, ≥25 kg/m² and <30, ≥30 kg/m² and <35, ≥35 kg/m²)
- Duration of diabetes (using the median as the cut-off)
- Race
- Ethnicity
- Country
- Region
- Baseline 1-hour PPG excursion
- Baseline 1-hour PPG (PPG ≤180 mg/dL, >180 mg/dL)
- Baseline 2-hour PPG excursion
- Baseline 2-hour PPG (PPG ≤180 mg/dL, >180 mg/dL)
- Prandial insulin dosing plan (carbohydrate counting, pattern adjustment)
- Type of basal insulin during the lead-in period (glargine, degludec)
- Number of prandial doses at study entry (<3, ≥3)
- SGLT-2 inhibitor treatment

Analyses for HbA1c and change from baseline in HbA1c will be performed using an MMRM model that includes the same fixed effects given for the primary analysis model plus factors of subgroup, 2-way interaction of subgroup and treatment, 2-way interaction of subgroup and visit, and 3-way interaction of treatment, visit and subgroup. The interaction of subgroup and treatment at the primary endpoint (Week 26) will be evaluated to assess the treatment by subgroup interaction. When analyzing HbA1c stratum (≤8.0%, >8.0%) as a subgroup, the baseline HbA1c will not be included as a covariate to avoid confounding.

Additional subgroup analyses may also be performed.

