5.3. Method of Assignment to Treatment

Patients who meet all criteria for enrollment will be randomized to double-blind treatment at Visit 8. Assignment to treatment groups will be determined by a computer-generated random sequence using an interactive web-response system (IWRS). Patients will be randomized to 1 of the 2 treatment groups in 1:1 ratio (double-blind LY900014 administered at meal time, double-blind insulin lispro administered at meal time). Stratification will be by country, HbA1c stratum ($\leq 8.0\%$, $> 8.0\%$ at Visit 7), and type of basal insulin during the lead-in period (glargine U-100 or degludec [U-100 or U-200]), and number of prandial doses at study entry (< 3 , ≥ 3).

Abbreviations: T = telephone visit; wk = week.

- a At Visit 2, patients treated with insulin aspart, insulin glulisine, regular insulin, or premixed insulin will be transferred to insulin lispro. At Visit 2, patients treated with a basal insulin regimen other than insulin glargine U-100 or insulin degludec will be transferred to an allowed study basal regimen of insulin glargine U-100 once or twice daily or insulin degludec U-100 or U-200 once daily. At Visit 8, patients will be randomized to either insulin lispro or LY900014 and continue their basal insulin regimen.
- b Titrate basal insulin.
- c Titrate prandial insulin (insulin lispro or LY900014).
- d Patients will discontinue study insulins at Week 26.
- e Eligible patients will have visits at approximately 3-month intervals for up to 26 weeks after Visit 801 for follow-up of insulin lispro antibody levels.

Figure 5.1. Illustration of study design.

6. A Priori Statistical Methods

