Table 6.2. Baseline and Post-Baseline Definitions and Patient Population by Study Period and Type of Analysis

Study Period/Analysis	Patient Population	Baseline Observations	Post-Baseline Observations
Lead-In Period			
TEAEs	All Enrolled Patients	Prior to first dose of open-label insulin lispro (or Visit 2 date if the dose date is missing)	The entire lead-in period after first dose of open-label insulin lispro and prior to the first dose of IP (or Visit 8 date if the dose date is missing).
Basal, prandial, and total insulin doses, and prandial/total insulin dose ratios continuous analysis	All Randomized Patients	Visit 2	Visits 3 to 8 prior to initiation of IP
Weight MMRM and ANCOVA	All Randomized Patients	Last of Visits 1-2	Visits 3–8 AND Last of Visits 3-8
26-Week Treatment Period (including Safety Follow-Up Visit where applicable)			
HbA1c MMRM and ANCOVA (efficacy estimand)	All Randomized Patients with a baseline and at least 1 post-baseline observation while on IP	Last of Visits 7-8	Visits 11, 13, 15, and 18 prior to discontinuation of IP AND Last of Visits 9-18 prior to discontinuation of IP
HbA1c ANCOVA (ITT estimand)	All Randomized Patients with a baseline and at least 1 post-baseline observation	Last of Visits 7-8	Visit 18 with imputation for patients who discontinue study prior to Visit 18
HbA1c categorical analyses longitudinal logistic regression and LOCF logistic regression	All Randomized Patients with a baseline and at least one post-baseline observation while on IP	Last of Visits 7-8	Visits 11, 13, 15, and 18 prior to discontinuation of IP AND Last of Visits 9-18 prior to discontinuation of IP
1-hr and 2-hr PPG and other MMTT variables (efficacy estimand)	All Randomized Patients with a post-baseline observation while on IP	Visit 8 prior to initiation of IP	Visit 18 prior to discontinuation of IP
1-hr and 2-hr PPG and other MMTT variables (ITT estimand)	All Randomized Patients with a post-baseline observation	Visit 8 prior to initiation of IP	Visit 18 regardless of IP use
10-point SMBG, basal, prandial insulin doses, prandial/total insulin dose ratios	All Randomized Patients with a baseline and at least one post-baseline observation	Visit 8 prior to initiation of IP	Visits 11, 13, 15, and 18 prior to discontinuation of IP AND Last of Visits 9-18 prior to discontinuation of IP

Baseline and Post-Baseline Definitions and Patient Population by Study Period and Type of Analysis

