6.2. Adjustments for Covariates

Stratification factors of this study include country, HbA1c stratum ($\leq 8.0\%$, $> 8.0\%$), type of basal insulin during the lead-in period (glargine or degludec), and number of prandial doses at study entry (< 3 , ≥ 3). Stratification factors will be entered into the IWRS for randomization and also collected in the database by electronic case report form (eCRF) or central laboratory. The analysis models will use the stratification factors as collected in the database.

For the primary analysis of HbA1c, the stratification factor of HbA1c stratum will not be included. Instead, the continuous value of baseline (Visit 8) HbA1c will be included in the analysis models.

For analyses of the incidence and rate of hypoglycemia, the baseline hypoglycemia event rate with the same category of the dependent variable will be included as a covariate in the analysis models.

Other efficacy analyses will include the stratification factors as noted in Sections 6.11 and 6.12.

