CCI [REDACTED], the primary efficacy comparison will be based on the contrast between LY900014 and insulin lispro at Week 26 (Visit 18) from the MMRM analysis of change from baseline in HbA1c including data collected from all randomized patients prior to permanent discontinuation of IP through Week 26 (efficacy estimand). The model for the analysis of the primary efficacy endpoint of change from baseline in HbA1c will include the fixed class effects of treatment, strata (pooled country, type of basal insulin, and number of prandial doses at study entry), visit, and treatment-by-visit interaction, as well as the continuous, fixed covariates of baseline value. An unstructured covariance structure will be used to model the within-patient errors. Significance tests will be based on LS means and Type III tests. If this analysis fails to converge, the following covariance structures will be tested in order:

- Toeplitz with heterogeneity
- autoregressive with heterogeneity
- compound symmetry with heterogeneous variances
- Toeplitz
- autoregressive
- compound symmetry without heterogeneous variances

The first covariance structure that converges will be used. The Kenward-Roger approximation will be used to estimate denominator degrees of freedom.

For both primary analysis approaches, LY900014 will be declared noninferior to insulin lispro if the upper limit of the 2-sided 95% CI for the LS mean difference in the change from baseline in HbA1c for LY900014 minus insulin lispro is below +0.4%. In addition, the 95% CI for the treatment difference will be compared to an alternative NIM of +0.3%. Both estimands will be tested at the full significance level of 0.05.

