6.13. Subgroup Analyses

6.13.1. Subgroup Analyses for HbA1c

The following subgroups will be analyzed for HbA1c if there are sufficient numbers of patients per group (for example, at least 10% in each group):

- age (<65 versus ≥ 65 years and <75 vs. ≥ 75 years and <65, ≥ 65 to <75, ≥ 75 to <85, ≥ 85 years)
- hemoglobin A1c stratum ($\leq 8\%$ vs. $> 8\%$)
- sex (male vs. female)
- body mass index (<25 vs. ≥ 25 , and <30 vs. ≥ 30 kg/m² and <35 vs. ≥ 35 kg/m²)
- duration of diabetes (using the median as the cut-off)
- race
- ethnicity
- country
- region
- baseline 1-hour PPG excursion (\leq baseline median, $>$ baseline median)
- baseline 1-hour PPG (PPG ≤ 180 mg/dl, > 180 mg/dl)

- baseline 2-hour PPG excursion (\leq baseline median, $>$ baseline median)
- baseline 2-hour PPG (PPG \leq 180 mg/dl, $>$ 180 mg/dl)
- type of basal insulin during the lead-in period (glargine vs. degludec)
- prandial insulin dosing plan (carbohydrate counting or pattern adjustment)
- number of prandial doses at study entry ($<$ 3 vs. \geq 3)
- sodium-glucose co-transporter 2 inhibitor treatment

Analyses for HbA1c and change from baseline in HbA1c will be performed using an MMRM model that includes the same fixed effects given for the primary analysis model plus factors of subgroup, 2-way interaction of subgroup and treatment, 2-way interaction of subgroup and visit, and 3-way interaction of treatment, visit and subgroup. The interaction of subgroup and treatment at the primary endpoint will be evaluated to assess the treatment by subgroup interaction. When analyzing HbA1c stratum as a subgroup the baseline HbA1c will be not be included as a covariate to avoid confounding. The subgroup interaction effect will be evaluated using a significance level of 0.10, unadjusted.

Additional subgroup analyses may also be performed.

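### The HbA1c-stratum subgroup model drops baseline HbA1c to avoid a confounding that cannot arise; keeping it, centred within stratum, is a small free improvement

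*SAP*

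**What the plan says.** Both documents list 17 subgroups for HbA1c, one of them the HbA1c stratum (at most 8% against above 8%). SAP 6.13.1 requests two responses: "Analyses for HbA1c and change from baseline in HbA1c will be performed using an MMRM model that includes the same fixed effects" as the primary analysis, plus subgroup, subgroup-by-treatment, subgroup-by-visit and three-way terms. The subgroup-by-treatment interaction at Week 26 is assessed at 0.10, unadjusted.

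The primary MMRM in SAP 6.11.1 contains "visit, and treatment-by-visit interaction, as well as the continuous, fixed covariates of baseline value", and SAP 6.2 explains why the stratum is left out of it: "Instead, the continuous value of baseline (Visit 8) HbA1c will be included in the analysis models".

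Only the HbA1c-stratum subgroup has an exception. SAP 6.13.1: "When analyzing HbA1c stratum as a subgroup the baseline HbA1c will be not be included as a covariate to avoid confounding". Protocol 10.3.5.2: "the baseline HbA1c will not be included as a covariate to avoid confounding". Neither document says what would be confounded.

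Randomization was stratified on HbA1c at Visit 7 (SAP 5.3). Baseline HbA1c for analysis is "Last of Visits 7-8" (SAP Table 6.2). Both precede the first randomized dose.

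**The concern.** Confounding needs a covariate associated with treatment assignment. Within a randomization stratum, a pre-treatment HbA1c value is related to treatment only by chance. The stated reason therefore gives no ground for removing baseline from the contrast that this analysis is meant to assess.

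Two things follow. First, one subgroup, defined by a randomization factor and closely tied to the endpoint, is tested with a less precise model than the other 16. Second, actual HbA1c and change from baseline, which give identical treatment contrasts when baseline is in the model, need no longer agree. A reader of the report could meet two interaction estimates, and sometimes two different verdicts at 0.10, for the same patients.

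**Working it through.** **1. The plan's own figure.** Margin 0.4, SD 1.1, 284 completers per arm (Protocol 10.1, SAP 5.2). SE = 1.1 × √(2/284) = 0.0923. Power = Φ(0.4/0.0923 − 1.96) = Φ(2.37) = 0.991, which agrees with the stated 99%. It concerns the primary comparison only. The documents give no figure for this subgroup, no baseline SD and no baseline-to-Week-26 slope, so the inputs below are assumptions.

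**2. What baseline overlaps with.** Stratum is a dichotomized HbA1c, so stratum and continuous baseline share information. That sharing affects the stratum main effect and the point at which LS means are evaluated. It does not involve treatment. If the analysis stratum is derived from the baseline value (SAP 6.7) and not from Visit 7, it is still pre-treatment.

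**3. Actual against change.** Let Y be HbA1c at a visit and B baseline, so change = Y − B.
- With B as a main effect, moving from Y to Y − B only lowers the coefficient of B by 1. All treatment contrasts and their SEs are identical. Centring B within stratum moves each stratum mean into the stratum term, so this still holds.
- Without B, and with complete data, the actual contrast minus the change contrast in a stratum equals the difference between arms in mean baseline (adjusted for the other model factors).

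**4. Size of that gap.** Assume baseline mean 8.0 and SD 0.75, so that the 8% cut halves each arm: 142 per arm per stratum.
- Within-stratum baseline SD: τ = 0.75 × √(1 − 2/π) = 0.452.
- Gap SD per stratum: 0.452 × √(2/142) = 0.054.
- Gap SD for the interaction: 0.054 × √2 = 0.076.

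Simulation gave 0.053 to 0.055 and 0.075 to 0.077. The 95% ranges are about ±0.10 and ±0.15 points.

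**5. Precision.** With slope β and residual SD σ, the interaction SE is s × √(4/142) = 0.168 s, where
- actual, no baseline: s = √(σ² + β²τ²)
- change, no baseline: s = √(σ² + (1 − β)²τ²)
- baseline in the model: s = σ

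For σ = 0.7:

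| β | actual | change | with baseline | SE reduction, actual / change |
|---|---|---|---|---|
| 0.3 | 0.120 | 0.129 | 0.117 | 1.8% / 8.9% |
| 0.5 | 0.123 | 0.123 | 0.117 | 4.8% / 4.8% |
| 0.7 | 0.129 | 0.120 | 0.117 | 8.9% / 1.8% |

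Simulated SEs agree to within 0.003. With σ = 0.9 the reductions run from 1.1% to 5.7%. As β approaches 1, the loss for change goes to zero.

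A wider set of assumptions was also tried: baseline mean 7.3 or 8.0, baseline SD 0.7 or 0.9, Week 26 SD 0.8 or 1.1, correlation 0.3 to 0.7, 670 patients. Dropping baseline multiplied the residual SD by 1.00 to 1.17 for change and 1.02 to 1.24 for actual. Gap SDs were about 0.05 to 0.07 per stratum and 0.065 to 0.092 for the interaction.

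**6. Effect on the interaction test.** In simulations of 670 patients (4,000 trials per setting), the two analyses without baseline disagreed at 0.10 in 7.6% to 9.0% of trials with no true interaction, and in 15% with a true interaction of −0.30. At correlation 0.5, power for −0.30 was 64.0% (actual) and 66.0% (change) without baseline, and 68.5% with it. The adjusted test kept its size (9.7% to 10.2%).

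One simulated four-visit MMRM data set with 14.5% missing at Week 26 showed the same pattern:

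| Model | Response | low stratum | high stratum | interaction (SE) |
|---|---|---|---|---|
| no baseline | actual | −0.101 | −0.202 | −0.101 (0.164) |
| no baseline | change | −0.128 | −0.213 | −0.084 (0.155) |
| with baseline | either | −0.120 | −0.210 | −0.090 (0.153) |

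**The case against.** The strongest defence is that the exception serves a purpose and confounding is only a loose word for it. With a common baseline covariate, default LS means for both strata are evaluated at the overall mean, near or beyond the edge of each stratum's own range. Dropping baseline avoids that. This is true, but centring within stratum avoids it too and leaves the treatment contrasts unchanged, so nothing has to be traded away.

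Other objections stand and limit the point:
- A reader might infer that the plan will report two different treatment effects with no way to choose between them. The documents do not support that. Protocol 10.3.5.2 aims the subgroups at the primary efficacy measure, and Protocol 9.1.1 defines that as change from baseline. Actual HbA1c is a companion, and both are unbiased estimates of one effect.
- A reader might infer that the model loses its main predictor. The stratum and stratum-by-visit terms remain. Under the assumptions in step 4, the stratum already absorbs 2/π, or 64%, of the baseline variance.
- The precision figures rest on assumed inputs, and for change the loss may be nil.
- The rule is prespecified and the same in both documents, so there is no contradiction between them.

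**Conclusion.** The stated reason is wrong and the exception should go, but the point is minor. Omitting baseline introduces no bias. It gives up about 1-9% of the interaction SE if the slope is 0.3-0.7, baseline SD 0.75 and residual SD 0.7-0.9. The loss could be larger under the wider assumptions, and is close to nil for change when the slope is near 1. That the actual and change estimates can differ does not depend on the slope: it follows from algebra whenever baseline is not perfectly balanced within stratum. The size of the difference depends on the assumed baseline SD and stratum split.

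It would be going too far to infer that a trial conclusion is at risk. This is one of 17 subgroups, tested without adjustment and outside the graphical testing scheme. H1-H4, alpha control, the sample size and the primary conclusions are unaffected.

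**What to change.** In SAP 6.13.1, delete the exception. Keep baseline HbA1c in the HbA1c-stratum subgroup model, centred within stratum, and take LS means at each stratum's own mean. State that change from baseline is the response to interpret.

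Because Protocol 10.3.5.2 contains the same exclusion, this reverses a protocol statement and is not a clarification. Record it in the SAP as a change with its justification. Protocol 10.3.1 and SAP 6.1 allow this without an amendment when no principal feature is altered, and one exploratory subgroup model is not a principal feature.

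The cost is a few lines of SAP text and one derived variable. The covariate is already collected and already in the primary model. The change should be made before unblinding. After that, the adjusted model can still be run beside the planned one, since SAP 6.13.1 permits additional subgroup analyses, but it should be labelled as added.

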6.13.2. Subgroup Analyses for Hypoglycemic Events

For the documented symptomatic hypoglycemia based on the thresholds of blood glucose \leq 70 mg/dL, the following subgroups will be analyzed:

- age ($<$ 65 vs. \geq 65 years and $<$ 75 vs. \geq 75 years and $<$ 65, \geq 65 to $<$ 75, \geq 75 to $<$ 85, \geq 85 years)
- hemoglobin A1c stratum (\leq 8% vs. $>$ 8%)
- region (Europe, North America, Eastern Asia [Japan, Taiwan, Korea], and other [India, Mexico, Argentina, Australia])
- type of basal insulin during the lead-in period (glargine U-100 vs. degludec U-100)
- prandial insulin dosing plan (carbohydrate counting or pattern adjustment)

The event rate and incidence will be analyzed using the same model specified in [Table 6.6](#) with the addition of factors for subgroup, and 2-way interaction of subgroup and treatment. The 2-way interaction will be used to evaluate treatment by subgroup interaction.

6.14. Interim Analyses and Data Monitoring

No interim analyses are planned for this study. If an unplanned interim analysis is deemed necessary, the appropriate Lilly medical director, or designee, will be consulted to determine whether it is necessary to amend the protocol.

6.15. Clinical Trial Registry Analyses

Additional analyses will be performed for the purpose of fulfilling the Clinical Trial Registry (CTR) requirements.

Analyses provided for the CTR requirements include the following:

- Summary of AEs, provided as a dataset which will be converted to an XML file. Both Serious Adverse Events and ‘Other’ Non-Serious Adverse Events are summarized by treatment group and MedDRA PT.
- An AE is considered ‘Serious’ whether or not it is a TEAE.
- An AE is considered in the ‘Other’ category if it is both a TEAE and is not serious. For each Serious AE and ‘Other’ AE, for each term and treatment group, the following are provided:
 - the number of participants at risk of an event
 - the number of participants who experienced each event term
 - the number of events experienced.
- For each Serious AE, these additional terms are provided for EudraCT:
 - the total number of occurrences causally related to treatment
 - the total number of deaths
 - the total number of deaths causally related to treatment.
- Consistent with www.ClinicalTrials.gov requirements, ‘Other’ AEs that occur in fewer than 5% of patients/subjects in every treatment group may be excluded if a 5% threshold is chosen. Allowable thresholds include 0% (all events), 1%, 2%, 3%, 4%, and 5%.
- Adverse event reporting is consistent with other document disclosures for example, the CSR, manuscripts, and so forth.

7. Unblinding Plan

The blinding and unblinding plan will be provided in a separate document stored in the Trial Master File.

8. References

- Computational Science Symposium Development of Standard Scripts and Programming Working Group. Analyses and Displays Associated with Measures of Central Tendency. Focus on vital Sign, Electrocardiogram, and Laboratory Analyte Measurements in Phase2-4 clinical Trials and Integrated Submission Documents. October 2013. Available at: http://www.phusewiki.org/docs/CSS%20White%20Papers%202016/CSS_WhitePaper_CentralTendency_v1.0.pdf. Accessed March 21, 2018.

Appendix 1. Empirical Estimation of Relative Event Rate

CCI

[Redacted text block]

[Redacted text block]

[Redacted text block]

[Redacted text block]

[Redacted text block]

[Redacted text block]

[Redacted text block]

[Redacted text block]

[Redacted text block]

[Redacted text block]

[Redacted text block]

[Redacted text block]

[Redacted text block]

[Redacted text block]

[Redacted text block]

[REDACTED] [REDACTED] [REDACTED] CCI [REDACTED]

[REDACTED]

[REDACTED]

[REDACTED]

[REDACTED]

Appendix 2. Statistical Analysis for Japan

Separate analyses will be performed for patients participating in Study ITRN from Japan based on 2 databases from:

- 1) Global database: the global database lock which will occur after all global cohort patients have completed Visit 801.
- 2) Japan database: the database lock which will occur after all Japanese patients who are enrolled into both global and MEE cohorts have completed Visit 801.

The analysis methods will be similar to those described for the main study. Statistical comparisons between treatment groups will be performed. Analysis models similar to the main study will be used without the model term for pooled country.

The analyses to be included will be documented in a separate list of analyses.

Appendix 3. Statistical Analysis for Maximum Extended Enrollment (MEE) Addendum

CCI

At least 1 patient from the indicated countries must be enrolled in the global cohort to be eligible for enrollment of subsequent patients into the MEE cohort. However, each indicated country should attempt to enroll approximately 10% of their target patient allocation in the global cohort before enrollment in the MEE cohort is started. The MEE addendum will not be implemented in these countries if the respective countries enroll sufficient number of patients in the global cohort to meet their local registration requirements.

CCI

All analyses are for descriptive purposes and are not for comparative purposes.

A subset of the planned efficacy, health outcomes and safety analyses, which are described in ITRN SAP sections above, will be produced for each country participating in the MEE addendum, with the exception of Japan (see Appendix 2 for a description of analyses for Japan). The analyses will be similar to those planned for the global cohort; however, no statistical comparisons between treatment groups will be performed. Analysis models similar to the global cohort will be used without the model term for pooled country. Least-Squares means and 95% confidence intervals will be displayed by treatment for the analysis of continuous variables.

The analyses to be included will be documented in a separate list of analyses.

Leo Document ID = 92138b2b-9d17-4eba-ba96-7a6ba5bc0457

Approver: PPD

Approval Date & Time: 24-Jul-2018 17:13:36 GMT

Signature meaning: Approved
